3.2 Recruitment, screening and informed consent procedure

The general practitioners will be invited to participate by post with a letter and information about QualiCCare and the project. There will be 10 practices per organisational structure. Each practice documents its diabetes patients based on their patient dossiers according to inclusion criteria. In order to participate in the study, patients will be informed about the study at the next follow-up and asked to sign a letter of consent to participate. A document will be available to the practices for patient information. Patients will be given sufficient time to decide whether to participate in the study.

The practice will receive CHF 50.00 per participating patient with documented score and free use of the diabetes management tool during the duration of the project. The medical services will be reimbursed according to usual tariff, Tarmed. In addition, the practice receives an evaluation of its practice performance compared to the overall collective.

The patient does not receive any financial compensation.

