2.4 Statistics and methodology

Statistical evaluation concept:

Primary endpoint:

Comparison of score baseline vs. 12 months using paired t-test.

Secondary endpoints:

Comparison of score changes between individual practices and practice networks using unpaired t-test.

Evaluation of the evaluation forms with regard to practical suitability and software by means of descriptive statistics.

In the previous two pilot studies, a measurable improvement in treatment quality could be measured in one and five primary care practices, respectively, with an increase in the score to 58 + 20 points. In order to achieve the goal of a relevant improvement of the overall score by a total of 10 points (from 56 to 66 points), 27 centres must be recruited with a significance level of 0.05 and a power of 80% (1). At a dropout rate of 10%, we will recruit 30 centers.

Methodology

Information of the primary care practices regarding the background and goal of the project by means of a letter and informative documentation.

Recruitment of primary care practices, divided into three different practice organisations (individual practices and group practices run on a private basis and with financial autonomy, as well as forms of joint practices with employed physicians without financial autonomy).

A signed contract between QualiCCare and participating primary care practices regulates the collaboration.

Procedure:

A baseline documentation takes place retrospectively from the training/workshop for the past 12 months, and a second, prospective documentation of the treatment is done during the following 12 months.

Training of the participating GPs and practice coordinator on the project including evaluation software, data entry and background to the criteria.

Documentation of the treatment quality of all patients with diabetes mellitus type 2 in a practice structure that meets the inclusion criteria according to the score criteria (baseline).

After 12 months, the treatment quality of the included patients with diabetes type 2 is recorded again using the same score.

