3. SUBJECTS AND STUDY PROCEDURES

3.1 Project population, inclusion and exclusion criteria

Reason for the number of patients:

In order to achieve the goal of a relevant improvement of the overall score by a total of 10 points (from 56 to 66 points), 27 centres must be recruited with a significance level of 0.05 and a power of 80%. The standard deviation of the total score in the individual practices is + 15, so that a patient population of > 50 patients per practice is necessary.

At a dropout rate of 10%, we will recruit 30 centers.

Inclusion and exclusion criteria:

Inclusion criteria:

All patients who have been diagnosed with type 2 diabetes mellitus according to their primary care provider, i.e. who have ever had HbA1c > 6.4% and/or are taking insulin and/or oral AD according to their patient dossier.

AND are at least 9 months in treatment with the same physician (in group practice in the same practice)

Exclusion:

Supervision <9 months in practice (change of practice, move, death, complete external supervision regarding DM, etc.)

Patients who do not agree to participate in the project

Patients for whom the doctor decides that they cannot participate in the project due to their illness (frailty, end of life).

All excluded patients will be anonymized and the reason for the exclusion will be stated. The excluded patients will not be considered for the evaluation.

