3.3 Study procedures

The duration of the project is 3 years, including recruitment and publication, i.e. from December 2017 until the end of 2020. After the recruitment of the primary care practices, training will take place in the form of an interprofessional workshop for the GPs and the responsible practice assistants on application and background of the score, as well as on its documentation in the tool. After the workshop, the practices will retrospectively create the baseline from their patient files. For the prospective data collection, the score criteria are recorded each time the patient visits the practice. In order to support the interprofessional cooperation with actors outside the GP's practice, the diabetes passport, revised by QualiCCare and distributed by Diabetesschweiz, can be used. Over a period of 12 months, all score criteria per patient must be recorded in the practice (primary endpoint). The project manager evaluates the difference between retrospective baseline and prospective score criteria documentation. The practices receive the evaluation of their practice and must answer a questionnaire to assess the recording tool with regard to practicability and suitability for practice. The results of the study will be published.

A selection bias may occur by not considering patients with difficult psychosocial problems, but since the patient collective is relevant and not the individual patient, this bias is not significant.

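### Consent is sought at a visit after the workshop but no visit is required in the baseline year, which can produce an apparent score gain; a sensitivity analysis in patients seen in both years would show it

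*Combined protocol and SAP*

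**What the plan says.** **Windows.** Section 2.4 anchors both years at the workshop: "A baseline documentation takes place retrospectively from the training/workshop for the past 12 months". The follow-up year, documented prospectively, starts where that one ends. Section 3.3 gives the order: "After the workshop, the practices will retrospectively create the baseline from their patient files".

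**Recording.** In section 3.3, "For the prospective data collection, the score criteria are recorded each time the patient visits the practice", and every criterion has to be recorded for each patient within those 12 months. No matching demand is made of the baseline year.

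**Entry.** Section 3.2 starts from the files: "Each practice documents its diabetes patients based on their patient dossiers according to inclusion criteria". Consent follows: "patients will be informed about the study at the next follow-up and asked to sign a letter of consent to participate". Section 3.1 excludes "Patients who do not agree to participate in the project" and leaves excluded patients out of the evaluation.

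**Eligibility.** Section 3.1 asks that patients "AND are at least 9 months in treatment with the same physician" (in a group practice, with the same practice). It separately excludes patients supervised for less than 9 months, including those whose diabetes is wholly managed elsewhere. The diagnosis can rest on a raised HbA1c at any time in the past.

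**Analysis.** There is no control group (section 2.3), and the primary comparison is a paired t-test (section 2.4). Section 2.5 covers dropouts but not a criterion with no entry. The only selection bias discussed, in section 3.3, concerns patients with psychosocial problems.

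**The concern.** The two windows are not treated alike. A listed patient who does not come back after the workshop cannot be asked, cannot consent and leaves both time points. A listed patient who stayed away during the baseline year and then returns can be asked and kept, possibly with a thin baseline record. The analysed set is therefore conditioned on contact in the second window only.

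If an unrecorded item counts as not met, this selection pushes the mean change upward even when care and attendance are stable. The planned paired comparison, having no control group, would count that shift as improvement from using the score.

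**Working it through.** **1. The plan's own figure.** The plan asks for 27 centres for a gain of 10 points (56 to 66) at a significance level of 0.05 and 80% power. With the practice as unit and the printed 20 read as the SD, n = (SD × (z_alpha + z_beta)/10)². One-sided this is (20 × (1.645 + 0.842)/10)² = 24.7, or 25; the exact t calculation gives 27 (power 0.812). Then 27/0.9 = 30. Two-sided with SD 20 gives 34, and SD 15 gives 20 (two-sided) or 16 (one-sided). Sidedness is not stated, but the present point does not change the centre count.

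**2. Apparent gain with unchanged care.** Assume that the score is averaged over patients, and let
- π = share of analysed patients with no baseline-year visit (not in the documents);
- r = fraction of the usual score still credited in a year without a visit (not in the documents);
- S = mean score in a year with a visit.

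The follow-up mean is S and the baseline mean is S × (1 − π(1 − r)). Setting the baseline mean to the plan's 56:

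gain = 56 × π(1 − r) / (1 − π(1 − r)).

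**3. Assumed visit patterns.** Each patient has the same visit rate in both years, and the patient is included only if seen in the second year.
- Poisson, mean m: π = e^(−m). For m = 4, 1.8%; for m = 6, 0.25%.
- Gamma-Poisson, mean m, shape k: π = [(k/(k+m))^k − (k/(k+2m))^k] / [1 − (k/(k+m))^k]. For m = 4, k = 2: (0.111 − 0.040)/0.889 = 8.0%. For m = 4, k = 4: (0.0625 − 0.0123)/0.9375 = 5.3%. For m = 6, k = 2: (0.0625 − 0.0204)/0.9375 = 4.5%.

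| Pattern | π | Gain, r = 0 | Gain, r = 0.5 |
|---|---|---|---|
| Poisson, mean 6 | 0.25% | 0.14 | 0.07 |
| Poisson, mean 4 | 1.8% | 1.0 | 0.5 |
| Gamma-Poisson, mean 6, shape 2 | 4.5% | 2.6 | 1.3 |
| Gamma-Poisson, mean 4, shape 4 | 5.3% | 3.2 | 1.5 |
| Gamma-Poisson, mean 4, shape 2 | 8.0% | 4.9 | 2.3 |

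For example, 56 × 0.08/0.92 = 4.9. If unrecorded items are left out of the score or carried forward, the gain can be near zero in every row.

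**4. What the full target would need.** A spurious 10 points requires π(1 − r) = 1 − 56/66 = 0.152. That is about 15% of patients with no baseline visit at zero credit, or about 30% at half credit.

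**5. Check by simulation.** One million patients were simulated with S = 60, zero credit, and 5% not visiting in each year independently. The change was +3.0 points among those with a follow-up visit. It was +1.5 if half of the non-visiting is permanent. It was 0.0 when all listed patients were scored in both years, and 0.0 among those seen in both years.

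**6. Effect on the test.** With 27 practices and a two-sided paired t-test at 0.05, a 3-point shift alone would be significant with probability 0.12, 0.32 or 0.85 if the SD of practice-level changes is 20, 10 or 5. These SDs are assumptions.

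**The case against.** **Baseline comes from files, not from visits.** Section 1 says the criteria also take in influenza vaccination and drug therapy, and current medication may stand in a file without a visit that year. Zero credit is therefore an upper bound. This stands, and it is why the range has to begin near zero.

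**The score belongs to the collective.** Sections 2.5 and 3.3 speak of the patient collective, and the sample size is counted in centres. A patient-averaged score is an assumption here, and a practice-level score built differently could respond differently. This also stands.

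**The 9-month rules may already imply contact.** Being in treatment or under supervision for 9 months can be read that way, and it will remove some patients with no baseline visit. But neither rule names a visit or a recorded value in the baseline year, so they limit the problem and do not close it.

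**The consent date is inferred.** No section dates the consent visit. The order of steps in sections 2.4, 3.2 and 3.3 makes the prospective year the natural reading, and nothing places it earlier.

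**Restricting the set has a price.** Bringing lapsed patients back may be a real benefit of using the score. An analysis limited to patients seen in both years leaves that out and moves away from section 2.4's aim of documenting all eligible patients in a practice. The zeros in the simulation follow by construction from equal visit rates and no true effect. This objection stands against making the restriction primary, but not against a sensitivity analysis.

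A reader might infer that the consent rule necessarily creates improvement and always favours it. The documents do not support that: both depend on how many patients lack a baseline visit and on how unrecorded items score, and neither is given.

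**Conclusion.** The asymmetry is real on the natural reading of the plan: entry needs a contact after the workshop, and nothing requires one in the year before. It can create an apparent improvement with no change in care, provided that items unrecorded in a year without a visit count as not met.

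Its size is an assumption. It is near 0 if such items are omitted or carried forward. With zero credit it is about 0.1 to 1 point under Poisson visits and up to about 3 to 5 points under the overdispersed patterns tried. A reader might infer that it could account for the whole 10-point goal. That would need about 15% of analysed patients without a baseline visit even at zero credit, and nothing in the documents indicates such a share. Nor is the shift beyond detection, since the practice files used for the baseline should show visit dates.

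This is a cheap improvement to the analysis plan. It does not show that the primary comparison is invalid.

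**What to change.** In section 2.4, pre-specify a key sensitivity analysis: repeat the primary paired comparison in consenting patients with at least one documented practice visit in the 12-month baseline window, mirroring the visit that consent guarantees at follow-up. State that the primary change will be interpreted as an effect of the score only if this analysis agrees, and say beforehand what counts as agreement. Report the numbers listed, asked, consented and without a baseline-year visit. A sentence in section 2.5 on how an unrecorded item is scored would show which end of the range applies.

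The cost is a few sentences and a little more extraction from files that are opened for the baseline anyway; the 27 and 30 centres are unchanged. The downside is that the restricted result applies only to patients seen in both years and omits any real gain from bringing lapsed patients back, so the two results should be shown together.

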3.3 Study procedures

The duration of the project is 3 years, including recruitment and publication, i.e. from December 2017 until the end of 2020. After the recruitment of the primary care practices, training will take place in the form of an interprofessional workshop for the GPs and the responsible practice assistants on application and background of the score, as well as on its documentation in the tool. After the workshop, the practices will retrospectively create the baseline from their patient files. For the prospective data collection, the score criteria are recorded each time the patient visits the practice. In order to support the interprofessional cooperation with actors outside the GP's practice, the diabetes passport, revised by QualiCCare and distributed by Diabetesschweiz, can be used. Over a period of 12 months, all score criteria per patient must be recorded in the practice (primary endpoint). The project manager evaluates the difference between retrospective baseline and prospective score criteria documentation. The practices receive the evaluation of their practice and must answer a questionnaire to assess the recording tool with regard to practicability and suitability for practice. The results of the study will be published.

A selection bias may occur by not considering patients with difficult psychosocial problems, but since the patient collective is relevant and not the individual patient, this bias is not significant.

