2.2 Primary and secondary endpoint(s)

Primary endpoint:

Change in score after use of this method to document care of patients with diabetes mellitus type 2 (baseline vs. 12 months)

Secondary endpoints:

Evaluation of the practicability of the score in different GP practice structures

Comparison of diabetes care (i.e. scores) between different organisational forms of practices (individual practices, group practices, practice chains)

Evaluation of the software for the evaluation of the score.

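### The plan has no step for obtaining the practicability questionnaire from practices that withdraw, so the ratings may come from completers only and may overstate practicability

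*Combined protocol and SAP*

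**What the plan says.** Section 2.2 lists two secondary endpoints that depend on the practices' own judgement: "Evaluation of the practicability of the score in different GP practice structures" and "Evaluation of the software for the evaluation of the score". Section 1 also names fitness for everyday practice as an aim of the project.

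The rating is described once, in section 3.3. The order there is: workshop, retrospective baseline, 12 months of prospective recording, the project manager's comparison of the two, and then "The practices receive the evaluation of their practice and must answer a questionnaire to assess the recording tool with regard to practicability". No interim or exit rating appears anywhere.

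The analysis in section 2.4 is one line: "Evaluation of the evaluation forms with regard to practical suitability and software by means of descriptive statistics". It gives no denominator and no rule for forms that are not returned.

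Section 2.4 also allows for losing practices: "At a dropout rate of 10%, we will recruit 30 centers". Section 3.1 repeats the allowance, and section 3.2 sets 10 practices per organisational structure. Section 3.4 deals with withdrawal of patients only. Section 2.5 says that dropouts are recorded, but its reason concerns the treatment-quality score. Section 7 makes the questionnaire an obligation in exchange for free use of the tool, without a date or a collection step.

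**The concern.** For most endpoints the loss of a centre is a nuisance. For practicability it may be the answer. A practice that stops because scoring is too laborious has shown that the method did not work there, and it is plausible, though not documented, that such practices are over-represented among those that leave.

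As written, the questionnaire is attached to the step at which a practice receives its comparison of baseline with the prospective year. A practice that stops early would have no full comparison to receive, so carrying out the plan step by step most naturally yields forms from completers. If those forms are then summarised without a stated denominator, a reader cannot see who is absent.

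The comparison across structures is the most exposed part. With 10 practices in each, a few losses concentrated in one structure could hide or reverse a difference that the endpoint is meant to show. A smaller matter is that a practice may rate the method just after learning how it performed, which could colour the answer.

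**Working it through.** **Inputs from the plan.** 27 centres needed and 10% dropout (sections 2.4 and 3.1); 30 centres recruited; 10 practices in each of 3 structures (section 3.2).

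**Reproducing the plan's figure.** 27 / (1 - 0.10) = 30, and 30 x 0.90 = 27. The 10% is therefore applied to centres and corresponds to 3 practices. How the 27 was derived does not matter for this point.

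**Inputs that the plan does not give.** q = share of completing practices that would rate the method practicable; d = the same share among practices that withdraw. Both are assumptions. The plan also does not define a practicable/not practicable outcome, so this dichotomy serves only to size the problem.

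**Overall overstatement.**
- Completers only: q
- All recruited: (27q + 3d) / 30
- Difference: q - (27q + 3d) / 30 = 0.10 x (q - d)

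| q | d | Completers only | All 30 | Overstatement (points) |
|---|---|---|---|---|
| 100% | 0% | 100% | 90% | 10 |
| 100% | 50% | 100% | 95% | 5 |
| 80% | 0% | 80% | 72% | 8 |
| 80% | 25% | 80% | 74.5% | 5.5 |
| 80% | 50% | 80% | 77% | 3 |
| any | equal to q | q | q | 0 |

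If withdrawn practices would rate higher than completers (d above q), the sign reverses.

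**Within one structure, if all 3 losses fall there.**
- Completers only: q
- All recruited in that structure: (7q + 3d) / 10
- Difference: 0.30 x (q - d)

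With q = 100% and d = 0, the structure is reported as 7/7 = 100% against 7/10 = 70%, a gap of 30 points. With 6 of the 7 completers satisfied and d = 0, it is 6/7 = 86% against 6/10 = 60%, about 26 points. The other two structures lose nothing in this scenario, so the same gap enters any comparison with them.

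**The case against.** Several stronger readings are tempting, and the documents do not support them.

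- A reader might infer that withdrawn practices are excluded from the questionnaire. The plan is silent on this. Section 7 ties the form to receiving the tool, not to finishing the year, so a practice that used the tool and stopped is arguably still bound. Section 2.4 also mentions a signed contract with each practice, whose terms are not in the documents. This stands against any claim of exclusion. It does not close the gap, because an obligation without a time point or a collection step does not secure the form.
- A reader might infer that practices rate the method only after seeing their results. That rests on one sentence in which receiving the evaluation and answering the form are joined by a plain conjunction, with no date for either. Rating after feedback can also be defended, since the practice evaluation is part of what participants receive and the software endpoint concerns software that produces the score.
- A reader might take the 10% as a forecast of practices giving up because of the burden. It is a sample-size allowance with no stated cause.
- A reader might count every practice that stops as a failure. Taken as the main rule, that would make silent withdrawals failures by definition and could replace an upward bias with a downward one.

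It is also fair that section 2.2 separates practicability of the score from evaluation of the software, while section 3.3 describes the form as assessing the recording tool. The form alone may not measure the score's practicability. That makes the share of practices completing 12 months of scoring more useful, because it bears directly on the score.

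Finally, the endpoint is descriptive, with no test or decision attached. The planned unpaired t-test between practice types concerns score changes and does not use the questionnaire.

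**Conclusion.** The concern holds as a gap in data collection and reporting, not as a demonstrated bias. The single rating described follows the 12-month recording and sits beside the practice's own evaluation, and nothing provides for obtaining it from the practices whose loss the plan itself allows for. Ratings may then come from completers only and may overstate practicability.

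The upper figures, 10 points overall and 30 in one structure, need every completer satisfied, every withdrawn practice dissatisfied and, for the second, all three losses in the same structure. The upward direction rests on withdrawn practices rating lower than completers, which is plausible but not documented; if they rate alike, there is no bias. The sizes also assume that losses match the 10% allowance.

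The change is worth making because practicability is a stated aim, the cost is small, and the missing ratings are hard to recover once practices have left. The primary analysis is unaffected.

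**What to change.** **Section 3.3.** Give the existing questionnaire, with a question on the reason for stopping, to any practice at the time it withdraws. Give it to all others at month 12, preferably before their results are handed over, and state that time point.

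**Section 2.4.** Report, by practice structure and beside the ratings, the number of practices recruited, the number completing 12 months of scoring and the number of forms returned. Use all recruited practices as the denominator, so that forms not returned are visible. Summarise the reasons for stopping. If practices that stopped are counted as finding the method not practicable, show this as a sensitivity display at most, not as the main result.

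**Cost.** About three extra mailings if losses match the allowance, and possibly a change in the order of two existing steps. No new instrument or staff is needed. The practicability figure may be less favourable, and some withdrawing practices will not reply, although they would still be counted among those recruited.

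### Section 3.3 sets aside an admitted selection bias because only the collective matters, yet the collective's mean is what selective omission can shift

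*Combined protocol and SAP*

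**What the plan says.** Section 3.3 raises the issue itself: "A selection bias may occur by not considering patients with difficult psychosocial problems". The same sentence closes it: "since the patient collective is relevant and not the individual patient, this bias is not significant". No figure, comparison of included with non-included patients, or sensitivity analysis supports that conclusion.

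Elsewhere the plan describes a complete population. Section 2.4 calls for "Documentation of the treatment quality of all patients with diabetes mellitus type 2 in a practice structure that meets the inclusion criteria". The inclusion criteria in section 3.1 begin "All patients who have been diagnosed with type 2 diabetes mellitus according to their primary care provider", subject to nine months with the same physician or practice. Section 3.1 then gives three grounds for exclusion:

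- too short a period of care in the practice;
- "Patients who do not agree to participate in the project";
- the doctor's decision that illness prevents participation, with frailty and end of life named.

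Section 3.4 ties exclusion during the project to the defined criteria. Section 3.1 requires a reason for each exclusion, and adds: "The excluded patients will not be considered for the evaluation".

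The design has no control group (section 2.3). Section 2.4 plans a paired t-test of the score at baseline and 12 months, and an unpaired t-test of score changes between individual practices and networks. Section 2.2 also lists a comparison of scores between practice forms.

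**The concern.** The dismissal confuses two things. Working with a group average makes the peculiarities of single patients matter less, because random error averages out. Non-random omission is different: it changes which patients the average describes. It leaves any one patient's score untouched and acts only on the summary that section 3.3 says is relevant.

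The project hypothesis in section 2.1 concerns treatment quality in a real-world setting and equivalence across practice structures. With no control group, extending the result to a practice's type 2 diabetes patients depends on who is included. Practices identify and approach the patients (section 3.2), so the omitted share could differ between practices and practice forms. If patients are passed over without a listed reason, the exclusion record in section 3.1 may not show it.

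**Working it through.** **The plan's own figures.** The plan gives no number for this bias. Its nearby figure, 27 centres for a 10-point gain, is reproduced by a paired t-test with an SD of change of 20 and one-sided alpha 0.05 (n = 27, power 81.2%); 27 / 0.90 = 30 centres after dropout. Sidedness and the SD of change are not stated, so the match rests on those assumptions. The bias formula below does not use this figure.

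**Bias in the primary result.** Let q be the share of eligible patients omitted, C_in the mean change in included patients and C_out the mean change the omitted patients would have had.

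- Change in the full collective = (1 − q) × C_in + q × C_out.
- The analysis estimates C_in.
- Bias = C_in − [(1 − q) × C_in + q × C_out] = q × (C_in − C_out).

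No sample size appears in this expression. The documents give neither q nor the difference, so both are assumed here. Bias in points:

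| q | difference −10 | difference 0 | difference +10 |
|---|---|---|---|
| 5% | −0.5 | 0 | +0.5 |
| 10% | −1.0 | 0 | +1.0 |
| 20% | −2.0 | 0 | +2.0 |

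The largest entry, 2 points, is one fifth of the 10-point improvement the plan calls relevant.

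**What averaging does.** With an assumed SD of change of 20, the standard error is 20/√27 = 3.85 for 27 units and 20/√1350 = 0.54 for 27 × 50 = 1350 patients (clustering ignored). A 2-point bias stays at 2 points. If the full collective truly did not change, a two-sided 5% test would reject 7.9% of the time with n = 27 and about 96% of the time with n = 1350. A larger collective therefore makes a fixed bias more consequential.

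**Baseline level.** The primary test uses within-patient differences, so a lower or higher starting level in omitted patients cancels. It cancels in the comparison of score changes too. Reported mean scores do not have this protection: their bias is q × (level in included − level in omitted).

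**Comparison of practice forms.** With forms A and B and difference in change d = C_in − C_out in each, the bias in B minus A is q_B × d_B − q_A × d_A. Assuming 5% omitted in A, 20% in B and the same d in both, this is 0.15 × d, or −1.5 to +1.5 points for d from −10 to +10. Unequal omission alone, with d = 0, does not bias the comparison of changes.

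**Fit with the criteria.** Psychosocial problems appear in none of the grounds in section 3.1 or 3.4, and the doctor's discretion is tied to illness. Refusal of consent is a listed ground, but it is the patient's act. Not considering a patient is not a listed criterion.

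**The case against.** The strongest reply is that section 3.3 only acknowledges a limitation. It says bias may occur and does not tell practices to leave anyone out. Listed or foreseeable routes can lead to the same absence: refusal of consent, or consent being sought only at the next follow-up (section 3.2), which can miss patients who do not attend. This stands, so a reader who inferred that the protocol authorises the omission would go too far.

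A reader might also infer that the improvement is overstated, or that the full collective would miss the 10-point goal. The documents do not support either reading. Both need an assumed smaller change in omitted patients; those with low scores could have more room to improve, and omission would then understate the change. The 10 points are a sizing goal, and no success threshold is stated.

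A third inference is that practices have a motive to drop difficult patients because they receive a performance comparison. Section 3.2 also pays CHF 50 per participating patient with a documented score, which pulls the other way. The net incentive is unknown.

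Finally, section 3.1 already asks for reasons for exclusion. That helps, but may not capture eligible patients who were simply not approached. None of these replies supports the assertion that the bias is not significant, which has no evidence behind it.

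**Conclusion.** The point holds in limited form. The justification in section 3.3 is invalid, and not considering these patients does not fit the population and exclusion rules in sections 2.4, 3.1 and 3.4.

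The estimate of change for all eligible patients is biased only if omitted patients would change differently. The comparison of practice forms is biased if, in addition, the product of omitted share and difference in change is unequal between forms. Reported score levels are biased if levels differ.

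Size and direction cannot be derived from the documents. The range of −2 to +2 points rests on assumed omission of 5–20% and an assumed difference in change of −10 to +10 points; it is zero if the changes are equal. The plan should be amended because it asserts an absence of important bias that it has no means of showing.

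**What to change.** 1. In section 3.3, delete the statement that the bias is not significant.
2. In section 3.1, state that psychosocial problems are not in themselves an exclusion reason, so these patients are listed and invited like all others. The existing criteria, including the right to refuse, stay as they are.
3. Extend the section 3.1 record to every eligible patient not included, in anonymised form, with the reason, including not approached or not seen.
4. Report the numbers eligible, excluded by reason and analysed, per practice and per practice form.
5. Add a sensitivity analysis to section 2.4: recompute the collective's change as (1 − q) × observed change + q × assumed change, with q from the record and a range of assumed changes. For example, with an observed change of 10 and q = 20%, assumed changes of 0, 10 and 20 give 8, 10 and 12. Zero change is one scenario and not a bound, since non-included patients could worsen or gain more.
6. Limit the conclusion to consenting, documented patients unless the result is robust across that range.

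The cost is some protocol wording, slightly more logging in the practices and one further analysis that needs only counts for the non-included patients. The headline may become narrower or less favourable.
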